APPENDIX R: ADVERSE EVENTS OR ERRORS DOCUMENT

Continuous glucose monitoring in adults - G1 study

Page 1

Adverse Events (or Errors)

Subject ID

Was this adverse event (or error) CGM related?

- Yes
- No

Start Date of the event:

Stop Date of the event:

Description of the event:

Outcome of the event:

- Data quality was affected
- Participant's well-being
- Other

Please describe the outcome(s):

(ex: cgm data is not accurate)

11/11/2024 7:49am

projectredcap.org

REDCap®

APPENDIX S: RESIDENTIAL HISTORY QUESTIONNAIRE

Residential History Questionnaire P4

Page 1

Please complete the survey below.

Thank you!

Project 4 G1 Study

Do you live at more than one home? [Vive en mas de una casa?]

- Yes [Sí]
- No [No]
- Prefer not to answer [Prefiero no contestar]

Average number of days spent per week at home #1 [Promedio de días pasados en casa #1]

- 1 day [1 día]
- 2 days [2 días]
- 3 days [3 días]
- 4 days [4 días]
- 5 days [5 días]
- 6 days [6 días]
- 7 days [7 días]
- Prefer not to answer [Prefiero no contestar]

Average number of days spent per week at home #2 [Promedio de días pasados en casa #2]

- 1 day [1 día]
- 2 days [2 días]
- 3 days [3 días]
- 4 days [4 días]
- 5 days [5 días]
- 6 days [6 días]
- 7 days [7 días]
- Prefer not to answer [prefiero no contestar]

What is your CURRENT HOME address? [Cual es su dirección actual?]

Street address: [Dirección:]

Town/City: [Pueblo/Ciudad:]

Zip Code (if known): [Código Postal (si lo sabe):]

APPENDIX T: P50 CDE SURVEY

P50 CDE v 1.5

Page 1

Please complete the survey below.

Thank you!

Version 1.5

Are you of Hispanic, Latino, Latina, or Spanish origin?
(Adapted from PhenX - ethnicity protocol [PX010502]/LOINC: 94158-3))

- No, NOT of Hispanic, Latino, Latina, or Spanish origin
- Yes, of Hispanic, Latino, Latina, or Spanish origin
- Prefer not to answer

If you selected, Yes, of Hispanic, Latino, or Spanish origin,

What part of Latin America, or Spain, are you from?

(Check all that apply)
(Adapted from: <https://worldpopulationreview.com/country-rankings/hispanic-countries>)

- Argentina
- Bolivia
- Chile
- Colombia
- Costa Rica
- Cuba
- Dominican Republic
- Ecuador
- El Salvador
- Equatorial Guinea
- Guatemala
- Honduras
- Mexico
- Nicaragua
- Panama
- Paraguay
- Peru
- Puerto Rico
- Spain
- Uruguay
- Venezuela
- Other
- Prefer not to answer

If other, please specify.

11/11/2024 7:50am

projectredcap.org

APPENDIX U: SATISFACTION SURVEY

CGM Satisfaction Survey

Page 1

Please complete the survey below.

Thank you!

The following are statements about your experience with the glucose device you wore. Report how much you agree or disagree with the statement shown.

The glucose monitoring system...

	Strongly Agree	Agree	Neutral	Disagree	Strongly Disagree
Helped me manage my weight.					
Made me think more often about my weight.					
Made me worry more than usual.					
Made me feel more frustrated than usual.					
Made me feel more down and depressed.					
Took too much time.					
Was too much of a hassle to use.					
Caused too much skin irritation or bruising.					
Was too painful to use.					
Gave me useful information.					
Helped me identify how food affects blood sugar.					

APPENDIX V: VIDEO EDITING PROGRESSION LOG

Participant ID	Video download	DV Transcript	Spanish Transcript	DV Transcript	English Transcript	Interview Spanish Transcript	Interview English Transcript
Gxxxx	Completed	Completed	Completed	Completed	Completed	Completed	Completed

APPENDIX U (APP. W): SAMPLE MOP MODIFICATION LOG (REPLACE WITH WHAT IS BEING USED)

MOP MODIFICATION LOG					
Section #	Version #	Date Modified	Page #	Text Location	Brief Modification Summary

APPENDIX ?: SAMPLE PROTOCOL DEVIATION LOG (REPLACE WITH WHAT IS CURRENTLY BEING USED) NO DEVIATION LOG FOR G1

Protocol Name: _____

Protocol Deviation Code:	Participant Initials	Participant ID#	Date Deviation Occurred: mm/dd/yyyy	Date Protocol Deviation Form Completed: mm/dd/yyyy	Contact Person (if applicable)

SAMPLE PROTOCOL DEVIATION CODES

Consent Form:

1. Missing or not obtained
2. Not signed and dated by participant
3. Does not contain all required signatures
4. Outdated, current IRB-approved version not used
5. Not protocol-specific
6. Does not include updates or information required by the IRB

13. Reportable serious adverse events not reported to IRB

Randomization:

7. Ineligible participant enrolled and/or randomized
8. Participant randomized prior to determining whether eligible for study
9. Occurs outside protocol window

IRB:

10. Not reporting a serious complication within 24 hours;
11. Approvals not kept up to date
12. Enrollment and/or treatment occurs prior to IRB approval or during period when on "on hold"

Participant

- 14. Receives wrong treatment
- 15. Visits occur outside expected follow-up window
- 16. Entered into another study

Study Data and/or Forms

- 17. Missing data and/or forms
- 18. Missing radiology and/or operative reports
- 19. Forms or data not sent from clinical site to coordinating center

## **List of Abbreviations**

AGP - Ambulatory Glucose Profile

BMI - Body Mass Index

CGM - Continuous Glucose Monitoring

CTSA - Clinical and Translational Sciences Institute

IPAQ - International Physical Activity Questionnaire

LME - Linear Mixed-Effects Model

LQMM - Linear Quantile Mixed Model

MAR - Missing at Random

MCAR - Missing Completely at Random

REDCap - Research Electronic Data Capture

SAP - Statistical Analysis Plan

## 1. Introduction

This document outlines the proposed analyses for Continuous Glucose Monitoring in Prediabetes (G1) study evaluating continuous glucose monitoring (CGM)-derived glycemic metrics among adults with prediabetes or prediabetes risk. The study employs a within-subject design without CGM masking, allowing for continuous measurement of glycemic variability while participants receive real-time glucose feedback at five-minute intervals via a smartphone application during CGM wear.

The purpose of this document is to describe the statistical analysis plan (SAP) for this study, including definitions of analysis populations, outcome measures, study time points, and planned statistical methods for summarizing CGM-derived outcomes and participant-reported narrative data.

## 2. Study Design

Study employs a within-subject design without CGM masking, enabling the measurement of glycemic variability, where participants receive feedback every 5 minutes while wearing the CGM device. This is an observational study where participant glycemic data is observed when CGM feedback is available on their smartphone app. This design captures continuous baseline values on the primary study outcome across 20 consecutive days while recorded video-based narratives are provided by participants each day as well as during the structured interview.

Glycemic variability. The primary outcome measure for the project is glycemic variability, which will be assessed using CGM automated data capture and the Dexcom Clarity cloud. We will utilize the Dexcom G6 Pro system (<https://provider.dexcom.com/products/dexcom-g6-pro/training-resources>) to capture glycemic variability over 14-20 complete wear days, with data recorded automatically every five minutes and timestamped. Participants will change the transmitter once on day 10, as the sensor has a wear time of 10 days. Data will be transferred to the Clarity cloud using an external Dexcom reader. Subsequently, the Clarity file will be exported and sent to the statistician for processing in RC software, where all variables for the complete ambulatory glucose profile (AGP) panel for glycemic variability will be calculated. Our main outcome analyses will focus on key variables related to glycemic control. Additionally, CGM data will allow us to generate important covariates, such as the % time worn by each participant per week and the number of times a participant changed the CGM sensor.

The study consists of four sequential timepoints. At baseline, participants complete an initial assessment prior to device use. Participants then wear a CGM sensor for a 10-day period (Phase A). At the end of the first wear period, the sensor is replaced per manufacturer instructions, followed by an additional 10-day CGM wear period (Phase B). Upon completion of the second wear period, participants complete a post-study assessment visit.

Figure 1 Flowchart of screening and inclusion process

\*NDSR was collected for P50 center-level analyses.

### 2.1. Sample size calculation

This was a single-arm pre-post study. Consistent with recommendations for pilot studies, a sample size of 20 participants was chosen to assess feasibility and estimate outcome variability (i.e., to characterize typical ranges and within-person variability and to assess data completeness/quality) rather than to formally test hypotheses. With limited prior data for this exact population and protocol, the most informative use of the pilot sample was to obtain preliminary estimates (means, SDs, and within-person variability) with enough data density

per participant to support planning. Sample size considerations were also informed by principles of data saturation commonly applied in qualitative research. These pilot-derived variance components were then intended to inform a powered sample size calculation for the subsequent study designed to test intervention effects on CGM outcomes.

### **3. Aims and Objectives**

Aim 1: To determine whether wearable CGM with smartphone feedback can improve glycemic control among individuals with prediabetes or prediabetes risk.

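### SAP Aim 1 asks whether CGM feedback improves glycemic control, but feedback is on in both periods being compared, so the primary analysis cannot answer it

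*SAP*

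**What the plan says.** SAP section 3 gives a single aim: "To determine whether wearable CGM with smartphone feedback can improve glycemic control among individuals with prediabetes or prediabetes risk". Section 1 says that "participants receive real-time glucose feedback at five-minute intervals via a smartphone application during CGM wear", and section 2 repeats that "participants receive feedback every 5 minutes while wearing the CGM device".

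Section 6.1 defines the primary outcome as the change in mean glucose between two successive 10-day wear periods and calls the first of them baseline. Section 8.2 compares Phase A with Phase B by a Wilcoxon signed-rank test. It then fits a linear mixed model with a Phase effect, a participant random intercept and a term Baseline_i. The text explains the random intercept and Phase but not Baseline_i. A p-value is to be reported.

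The SAP uses the word baseline in three ways:
- before the device: "At baseline, participants complete an initial assessment prior to device use" (section 2);
- all of wear: "This design captures continuous baseline values on the primary study outcome across 20 consecutive days" (section 2; the same sentence is in protocol 3.8);
- the first wear period (section 6.1).

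Section 2.1 says "This was a single-arm pre-post study". It explains that 20 participants were chosen for feasibility and variability "rather than to formally test hypotheses", and that the pilot "variance components were then intended to inform a powered sample size calculation for the subsequent study designed to test intervention effects on CGM outcomes".

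**The concern.** Asking whether feedback improves glucose requires glucose with feedback to be set against glucose without it. The planned contrast sets feedback against feedback. A change from baseline in a pre-post study reads as before versus after feedback, but the first period is already under feedback.

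This is the SAP's only aim and its primary outcome. A null result could be reported as evidence against feedback that had worked fully in the first days. A fall could be reported as improvement caused by feedback when it reflects time since first wear or a sensor or arm difference. A larger sample would narrow the interval without changing what is estimated. Both the aim and the reported p-value also sit badly with section 2.1, which disclaims hypothesis testing and leaves intervention effects to a later study.

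**Working it through.** **1. Is there any feedback-free glycemic value to compare with?**

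| Source | Feedback status |
|---|---|
| Phase A CGM (SAP 2, 6.1) | on |
| Phase B CGM (SAP 2, 6.1) | on |
| Dexcom glucose marked at the baseline visit (protocol 3.8, Appendix F) | sensor is applied at that visit and shows nothing until warm-up ends (protocol 3.13.2); Day 1 is excluded (SAP 8.1) |
| Dexcom glucose marked at the post visit (same tables) | the visit follows removal of the second sensor (protocol 3.13.3) |
| A1c | measured at baseline, not at the post visit (protocol 3.17.4, Appendix E) |
| Masked run-in or control arm | none (protocol 3.12; SAP 2.1) |

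So no feedback-free value of the outcome exists, and there is no before/after A1c pair.

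**2. What B minus A estimates.** Let F be the full feedback effect, f(t) the fraction present on wear day t, and T(t) any time trend or sensor difference. Then

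B − A = F × [mean f over B − mean f over A] + [mean T over B − mean T over A].

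The aim needs F. The contrast gives F times a share that is unknown, plus a nuisance term.

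**3. Size of the share.** Applying the SAP 8.1 exclusions to full wear gives A = days 2–9 (mean day 5.5) and B = days 11–19 (mean day 15). The profiles are assumptions.

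| Assumed onset of effect | Share of F seen in B − A |
|---|---|
| Immediate, constant | 1 − 1 = 0% |
| Exponential, 2-day half-life | 19% (t = day) to 23% (t = day − 0.5) |
| Linear to day 20 | (15 − 5.5)/20 = 47.5% |
| Linear, complete by day 14 | 56% to 58% (same two conventions) |
| Step at day 7 | 1 − 3/8 = 62.5% |
| Step at day 10 | 1 − 0 = 100% |
| Step at day 15 | 5/9 − 0 = 56% |
| Immediate, fading linearly to zero by day 20 | (1 − 15/20) − (1 − 5.5/20) = −47.5% |

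On full windows (days 1–10 and 11–20) the same profiles run from −50% to 90%. A step at day 15 and a ramp complete by day 14 give almost the same share, so the contrast cannot be scaled back to F.

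**4. Behaviour of the planned Wilcoxon test.** Simulation with n = 20, 3,000 runs, and assumed between-person and daily SDs of 8 mg/dL each:
- Immediate effect of −5 mg/dL: mean B − A is 0.0, with rejection in 4.8% of runs, the same as with no effect at all.
- No effect but a drift of −0.3 mg/dL per day: −0.3 × 9.5 = −2.85, with rejection in 85% of runs.
- Immediate effect of −5 with a drift of +0.3 per day: expected B − A is +2.85, the wrong sign.

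The SAP gives no alpha, power, effect size or SD behind N = 20, so there is no planning figure to reproduce.

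**5. Baseline_i read as the Phase A mean.** Section 6.1 makes this a natural reading. Assume equal phase variances s² and A–B correlation r.
- Variance of the person mean given A: s²(1 − r²)/4.
- Half the within-person variance: s²(1 − r)/2.
- Implied random-intercept variance: s²(1 − r²)/4 − s²(1 − r)/2 = −s²(1 − r)²/4, which is never positive, so it is estimated at about zero.

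For s² = 100 and r = 0.5, 0.7, 0.86 the implied values are −6.25, −2.25 and −0.49. In simulation (n = 20, 300 runs each) the median random-intercept variance was 46, 67 and 82 without Baseline_i, and 0.00 with it. The Phase estimate was identical either way.

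**The case against.** The best defence is that the SAP largely discloses this. It calls the study observational, single-arm and a pilot, disclaims formal testing and defers intervention effects. On that view the defect is one over-strong sentence, and no planned estimate is miscalculated. The description is fair. But the over-strong sentence is the only aim, and section 8.2 still attaches a hypothesis test to it.

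Second, the contrast is informative about something. Protocol section 2 expects learning within 20 days, and change from earlier to later feedback days bears on gradual learning, although confounded with time. This stands, and the restated aim keeps exactly that quantity. The limitation sentence proposed below rules out only conclusions about feedback versus no feedback.

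Third, the two sensors differ less than they might. Protocol 3.13.2 and Appendix H have the participant apply both with staff guidance. The differences are in-person versus Zoom guidance, the arm and the device unit. These are possible confounders, not demonstrated biases. The exclusions in SAP 8.1 limit transition artifacts but do not separate phase from sensor.

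Fourth, Baseline_i may stand for a pre-device covariate, since section 8.2 also lists baseline age, sex and BMI. That is possible. The variance result is therefore conditional on one reading, and it is secondary to the main point. Planned descriptive SDs would still show between-person spread.

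Finally, the shares assume full wear, whereas the plan allows 14–20 days overall and requires only 2 valid days per period. The planned daily traces might help tell a step from a ramp, but they could not reveal an effect already present when readings begin.

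**Conclusion.** The aim and the primary analysis do not match, and this must be fixed. That conclusion rests on the documents alone: feedback is on in both phases, there is no comparator, and A1c is not repeated. The sizes rest on assumed profiles. The share of a true effect that shows in B minus A ranges from −47.5% to 100%, and an immediate, lasting effect gives zero. Neither a null nor a non-null result supports a conclusion on Aim 1. The loss of the between-person variance component applies only if Baseline_i is the Phase A mean. In that case it undercuts the planning purpose stated in section 2.1.

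**What to change.** Issue a dated SAP amendment with its rationale. Protocol 3.6 puts the final screening at August 30, 2024, so the amendment should state whether CGM outcome data had been seen.

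1. Section 3: restate Aim 1 as *To estimate the change in mean glucose from the first to the second 10 days of unmasked CGM wear.*
2. Section 6.1: define the outcome as change from Phase A to Phase B, and call the first period Phase A instead of baseline.
3. Section 2, and the same sentence in protocol 3.8: delete the word baseline from the description of the 20 days of values.
4. Section 2.1: add *No CGM glucose is available before feedback began, so pre-post does not describe the CGM outcome.*
5. Section 8.2: remove Baseline_i. Because section 7 requires data in both periods, removal leaves the mixed-model Phase estimate unchanged. If the term is kept, define it as a measure taken before device use, such as baseline A1c. It must not be the Phase A mean, which is already an outcome value in the model.
6. Section 8.2: add *The Phase A to Phase B contrast does not estimate the effect of CGM feedback versus no feedback, and neither a null nor a non-null result supports a conclusion about it; its p-value is exploratory.*

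The cost is one amendment and one word in the protocol, with no new data or participants. The stated claim becomes weaker. Protocol 3.25.1 sends participants to a public registry for results, so the wording there should be checked for consistency. Two related conflicts need separate action: protocol section 2 states a different Aim 1 (making the video clips), and SAP section 2 names glycemic variability as the primary outcome.

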### **4. Demographics and Baseline Assessments**

The following are specific demographic / baseline assessments of interest for analyses.

- 1) Age
- 2) Sex
- 3) Ethnicity (NIH/OMB)
- 4) Race (NIH/OMB)
- 6) Highest level of education
- 7) Current employment status
- 8) Total household income
- 9) Health insurance
- 10) CDC prediabetes risk score
- 11) Body Mass Index (BMI)
- 12) Physical Activity Level (International Physical Activity Questionnaire [IPAQ])
- 13) Finger prick HbA1c (%)
- 14) Self-reported history of prediabetes

### **5. Data Storage**

Data will be collected and managed using Research Electronic Data Capture (REDCap) housed at University of Southern California's Clinical and Translational Sciences Institute (CTSI) and Dexcom Clarity. REDCap is a secure, web-based application designed for research studies that provides an intuitive interface for validated data entry, audit trails for tracking data manipulation and export procedures, and automated export procedures for seamless data downloads to common statistical packages, and procedures for importing data from external sources.

### **6. Outcomes**

#### **6.1. Primary outcome**

Change in mean glucose (mg/dL) from baseline. Mean glucose will be derived from CGM data obtained from the Dexcom Clarity system. Raw glucose values will be processed and analyzed using the R statistical software package *iglu* to generate the full CGM variability metrics panel. For each participant, mean glucose will be calculated as the average of all valid CGM glucose readings within each 10-day assessment period. The outcome measure represents the change in mean glucose between the baseline 10-day assessment period and the subsequent 10-day period.

#### **6.2. Other pre-specified outcome**

Videos obtained from informal and semi-structured interviews (total minutes).

### 6.3. Safety outcomes

#### Adverse events

Adverse events are reported by participants or occasional assessment.

## 7. Analytic Dataset

Primary analyses will include participants with sufficient CGM data; inclusion required at least 2 days of valid CGM data within each 10-day assessment period. Descriptive analyses for other pre-specified outcome will include all participants that provided at least 1 video.

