The research staff will send a text message to the participant to remind them the date and time they scheduled the sensor replacement 48h before the sensor replacement. The research staff will conduct a Zoom phone call with each participant on day 10 to assist with sensor replacement. The replacement Zoom will be scheduled during the baseline visit. Additionally, participants will be asked about any adverse events related to the CGM sensor as listed on the RC survey form, including inputting AE and SAE. Three days before the scheduled call, the research staff will send each participant a G6-Pro application video tutorial. On the 10th day of wearing the CGM, the research staff will meet with participants via Zoom to guide them through the process of changing the G6-Pro sensor. During this meeting, the research staff will provide a step-by-step explanation of the sensor replacement procedure, allowing participants to ask any questions they may have and receive support from the research team. Participants will be reminded not to discard the used transmitter-sensor; instead, they will be instructed to place it in the envelope provided by the research staff during the baseline visit.

Before the zoom call takes place, the study staff will login into their RC account and select the G1-Study project to be able to access the participants' charts of the G1-Study. After the website takes the staff to the study page, the staff will select the tab called "Record Status Dashboard" found on the left hand of their screen. The platform will then show the list of each participant and with each form/survey involved in each phase of the study. For this activity, the study staff will choose the only survey found on the "CGM Phase" column. The study staff will have this survey open throughout the zoom call and will complete the form after the participant has successfully removed the old sensor and replaced the new G6 PRO sensor. An example of the Sensor Replacement Telephone script is provided in the Appendix _H_.

Compensation

For the CGM phase, each participant will receive \$200 compensation, which will be given as gift cards. The first \$100 gift card is assigned to the first 7-10 days of successful wear, and \$100 is applied to the second 7-10 days of wear after replacement. Both gift cards are given to the participant at their post visit.

Post-Visit

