3.22.2 Data and Form Checks

Data and form checks depend upon the complexity of the study. Data quality control checks may identify potential data anomalies such as:

- *Missing data or forms*

- *Out-of-range or erroneous data*
- *Inconsistent and illogical over-time dates*
- *Fields on a "completed form" are actually not completed; or no reason for missing data is provided.*

If the study is using electronic data forms, provide a summary of data and form checks that will be implemented for data quality control.

CGM data will be checked periodically throughout the week by study statistician and study staff via Dexcom Clarity to ensure participants' CGM data is being transmitted. If there are any gaps in the data, study staff will contact participants to obtain information on reasons for missing data and resolve any issues within the next day (connectivity, sensor error and failure, etc.). At the post visit, study staff will collect participants' transmitters. Data from transmitters will then be uploaded into Clarity using readers to ensure CGM data completeness.

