## 8. Statistical Analyses

### 8.1. Analytic oversight and preprocessing.

Descriptive statistics will summarize participant characteristics and outcomes (means  $\pm$  SD or medians [IQR]; proportions for categorical variables). Prior to modeling, distributions will be visualized to assess skewness/kurtosis; influential points will be evaluated (Cook's distance, DFBETAs) and addressed via winsorization or removal with justification. Outlier handling decisions will be documented a priori in the analysis plan. For CGM variable generation, raw 5-minute glucose values (excluding Day-1, replacement, and removal days to minimize calibration/transition artifacts) will be used for visualization (daily traces; AGP-style plots) and processed with the *iglu* R package to derive standardized metrics.

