### 8.2. Primary outcome.

For the primary outcome of mean glucose (mg/dL), we will first perform a Wilcoxon signed-rank test to compare paired mean glucose values between Phase A and Phase B, and then fit a linear mixed-effects model (LME) to estimate within-person change from Phase A to Phase B while accounting for repeated measures:  $Y_{ij} = \beta_0 + \beta_1(\text{Baseline}_i) + \beta_2(\text{Phase}_j) + \eta_i + \varepsilon_{ij}$  where  $\eta_i$  is a participant-level random intercept and Phase is categorical (A vs B). If assumptions are not met (e.g., skewed residuals), we will fit a linear quantile mixed model (LQMM) as a robust alternative. Candidate covariates (pre-specified) include baseline age, sex, and BMI. Note that additional exploratory analyses may be conducted to examine other demographic variables and baseline characteristics as covariates by assessing their potential associations with CGM outcomes. Variance inflation factors will be examined to rule out multicollinearity. Results will be reported as model-based estimates, corresponding 95% confidence limits, and p-value of the corresponding hypothesis test. All analyses will be performed in R ( $\geq 4.5.1$ ).

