## 9. Missing Data

Missingness will be characterized (MCAR/MAR) and addressed using likelihood-based methods and, if needed, multiple imputation or inverse probability weighting; sensitivity analyses will compare approaches.

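### SAP 7 confines the mixed model to participants with both CGM periods, so the likelihood-based missing-data handling in SAP 9 has no missing period to act on

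*SAP*

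**What the plan says.** SAP 7 sets one rule for the primary analyses: "inclusion required at least 2 days of valid CGM data within each 10-day assessment period". SAP 8.2 places two analyses under the primary outcome. The first is a Wilcoxon signed-rank test of Phase A against Phase B. The second is to "fit a linear mixed-effects model (LME) to estimate within-person change from Phase A to Phase B while accounting for repeated measures", with a Baseline term, a categorical Phase term and a random participant intercept. The outcome is one value per person and phase: under SAP 6.1, "mean glucose will be calculated as the average of all valid CGM glucose readings within each 10-day assessment period".

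SAP 9 says that missingness will be "addressed using likelihood-based methods and, if needed, multiple imputation or inverse probability weighting; sensitivity analyses will compare approaches". It names no analysis set for any of these methods.

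SAP 8.2 does not define Baseline. SAP 6.1 gives that name to the first 10-day CGM period, while SAP 2 uses it for the assessment before the device is worn.

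On the purpose of the pilot, SAP 2.1 says: "These pilot-derived variance components were then intended to inform a powered sample size calculation". It does not say which analysis supplies those components.

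**The concern.** A mixed model is useful with incomplete repeated measures because a participant with only one period still contributes. SAP 7 removes such participants before the model is fitted. The plan therefore promises likelihood-based handling in one section and takes away its material in another. If loss of Phase B is related to Phase A glucose, the paired estimate is biased by regression to the mean, and the planned model could have avoided this.

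A secondary question concerns planning. With one mean per person and phase, the model's residual combines how a person's level differs between phases with day-to-day noise averaged over the days worn. If the next study uses a different wear time, its sample size needs the two parts separately.

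**Working it through.** **Nothing to reproduce.** The sample size of 20 is justified as a pilot; SAP 2.1 gives no SD, effect size or dropout rate. All variances below are assumptions: day-to-day SD s of 6-14 mg/dL, participant-by-phase SD τ of 3-5, independent days, total Phase A SD 12, n = 20. SAP 8.1 works on data "excluding Day-1, replacement, and removal days to minimize calibration/transition artifacts", so full wear leaves about 8 usable days in Phase A and 9 in Phase B.

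**1. Complete pairs.** With both means present for everyone, the random-intercept estimate of the phase effect equals the mean paired difference. In one simulated data set both were -3.184 with SE 1.296. Adding the Phase A mean as Baseline left the estimate at -3.184.

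**2. Bias of the paired set if loss depends on Phase A glucose.** Let ρ be the correlation-type slope of the Phase B mean on the Phase A mean. Then

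bias = (1 - ρ) × (Phase A mean of all - Phase A mean of those retained), with 1 - ρ = (τ² + s²/8)/12².

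For τ = 5, s = 10: 1 - ρ = (25 + 12.5)/144 = 0.26. With 20% lost at odds ratio 4 per SD, integrating the logistic loss model over a normal Phase A distribution puts those retained about 2.6 mg/dL below the full group. The bias is 0.26 × 2.6 = 0.68.

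Simulation for the same case:

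| Analysis | Bias (mg/dL) | SE |
|---|---|---|
| Paired set | 0.67 | 2.10 |
| Inverse probability weighting | 0.13 | 2.27 |
| Random-intercept model, all available periods, no Baseline term | 0.00 | 2.15 |

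Over all cases (10-20% lost, odds ratio 2-4) the paired-set bias is about 0.1-0.9, with SE 1.2-2.5. Under random loss, using all periods gains at most about 4% of variance.

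**3. Why the Baseline term matters.** Suppose Baseline is the Phase A mean. The random-intercept variance then collapses to about 0, and the phase estimate on all available periods is

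mean B (retained) - mean A (all) + b₁ × [mean A (all) - mean A (retained)].

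This is unbiased when b₁ = ρ and equals the paired difference when b₁ = 1. In the Phase A rows the outcome is the covariate itself, so those rows pull b₁ toward 1. Simulation leaves 0.44 of 0.68 mg/dL (65%) for s = 10, and 0.60 of 0.91 (66%) for s = 14, both with τ = 5. The wider set therefore works only without that term.

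**4. Variance components.** Without the Phase A mean as covariate, the period-mean model does separate between-person variance (mean estimate 99.7, truth 100) from pooled within-person variance (27.2, expected 27.8). It cannot split the latter, which is τ² + s²/days. For planning, Var(change) = 2τ² + s²(1/dA + 1/dB):

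| | 8+9 days | 5+5 days | 14+14 days |
|---|---|---|---|
| τ 5, s 6 | 58.5 | 64.4 | 55.1 |
| τ 3, s 14 | 64.3 | 96.4 | 46.0 |

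A sample size based on the 8+9 variance is 9% (58.5/64.4) to 33% (64.3/96.4) too small for 5+5 days. It is 6% (58.5/55.1) to 40% (64.3/46.0) too large for 14+14 days, and right for the same wear.

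**The case against.** **One-period participants may not exist.** The protocol plans for 20 retained participants. Its data checks say "If there are any gaps in the data, study staff will contact participants to obtain information on reasons for missing data", and in Protocol 3.13.2 the first CGM-phase gift card "is assigned to the first 7-10 days of successful wear". The causes of gaps named in Protocol 3.22.2 are technical, which suggests loss unrelated to glucose. This stands: the glucose-dependent loss is an assumption. A reader might infer that the primary result is biased; the documents do not support that.

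**SAP 9 already lists imputation and weighting, with comparisons.** This stands in part. SAP 7 excludes people from the primary analyses without discarding their data, so weighting could draw on their Phase A records. But both methods are conditional, and no section says who enters them.

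**The planning point can be overstated.** A reader might infer that the model cannot separate variance components at all. It does separate between-person from pooled within-person variance. SAP 2.1 asks only for within-person variability, without fixing its level, and SAP 6.1 also derives a panel of variability metrics from the raw readings. What remains is the narrower statement that the participant-by-phase and day-to-day parts are not split. No document gives the next study's wear, so harm to its sample size is conditional.

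**The 2-day minimum.** A reader might also infer that very short records distort the estimate. Unequal wear alone does not bias the mean change, and SAP 2 plans 14-20 complete wear days, so 2-day records may be rare.

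**Conclusion.** The inconsistency between SAP 7 and SAP 9 is real and follows from the text alone: as written, the mixed model is a complete-pair analysis. Its numerical effect is modest and rests on assumed variances and an assumed loss mechanism: about 0.1-0.9 mg/dL, always below one standard error, falling to about 0 after the change; at most about 4% of variance under random loss; and nothing if everyone has both periods. In a pilot of 20 that does not set out to test hypotheses formally, the change is worth making because it is nearly free, not because the result is shown to be wrong.

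Removing a Phase A Baseline term is a necessary part of the remedy, and it alters the model written in SAP 8.2. The variance-component point is secondary and optional; it matters only if wear per period differs in the next study.

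**What to change.** 1. **SAP 7 and 8.2.** Keep the paired set for the Wilcoxon test. Fit the mixed model to every participant with at least 2 valid days in at least one period, and report the paired-set mixed model as a sensitivity analysis.
2. **SAP 8.2.** Define Baseline. If it is Phase A mean glucose, omit it from this model: Phase A is already an outcome, most of the bias would otherwise remain, and a participant with only Phase B would be dropped for a missing covariate. Record this as a change to the written model.
3. **SAP 9.** State which participants enter the likelihood, imputation and weighting analyses.
4. **Optional, for SAP 2.1.** Add a dated supporting mixed model on daily mean glucose after the SAP 8.1 exclusions, with a fixed Phase effect and random participant and participant-by-phase effects. Report the components with intervals. At n = 20 the participant-by-phase part will be imprecise: with day SD 10 and full records, a true SD of 3 is estimated between 0 and 5.0, and a true SD of 5 between 2.3 and 7.2 (95% ranges).

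The cost is a few sentences and a few lines of code on data already held. The downsides are a little more analysis and estimates that may differ between sets if wear relates to response. Protocol 3.6 puts the final screening in August 2024, so date the change and state whether outcome data had been seen.
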